**Study 111-301 Statistical Analysis Plan**

- TAb cross reactivity by subject and cardiac disorder or HLGT 'fluid and electrolyte imbalance' related adverse event.
- Mean antibody titers and AGV

All immunogenicity listings will be ordered by treatment group, 4-digit subject number (i.e., the subject ID, excluding the site number) and visit.

**Study 111-301 Statistical Analysis Plan****20 PHARMACOKINETICS AND PHARMACODYNAMICS**

BMN 111 concentrations and pharmacokinetic (PK) parameters will be summarized descriptively by visit for all subjects in the PK population. If supported by the data, the exposure-response relationship between BMN 111 exposure and immunogenicity, efficacy, biomarker, and safety pharmacodynamic (PD) endpoints of interest will be explored. Details of the PK/PD analyses are separately documented in the Clinical Pharmacology Analysis Plan.

22 SUMMARY OF CHANGES TO STUDY SAP

Version		Affected Section (Number of Section in Previous SAP)	Summary of Revisions
Number	Date		
Final SAP	05-Nov-19	1.0 (NA)	Signature page added.
Final SAP	05-Nov-19	4.6.2 (2.6.2)	The Japanese randomization has been described in more detail.
Final SAP	05-Nov-19	5.1.2 (3.1.2)	Gonadotropin-releasing hormones have been added as an exclusion from the Pre Protocol analysis population.
Final SAP	05-Nov-19	5.4 (3.4)	111-901 analysis visit windows have been updated.
Final SAP	05-Nov-19	5.4 (3.4)	A spaghetti plot of standing height Z-scores has been added.
Final SAP	05-Nov-19	8.0 (6.0)	A listing of major deviations classified as “dosing irregularity” has been added.
Final SAP	05-Nov-19	9.0 (7.0)	Baseline characteristics growth measures are re-ordered. Tanner Stages, other than (I,>I) are not included in baseline summary.
Final SAP	05-Nov-19	10.0 (8.0 and Appendix)	Details of Achondroplasia-related terms are removed from the SAP appendix, and located in a study file.
Final SAP	05-Nov-19	10.0 (8.0)	Physical exam results listing added.
Final SAP	05-Nov-19	11.0 (9.0)	The concomitant medications are to be summarized by ATC level 2, not 4.
Final SAP	05-Nov-19	13.0 (11.0)	Definition for missed dose has been added. Dose interruptions have been replaced with a summary of “Reasons for missed dose”.
Final SAP	05-Nov-19	14.0 (12.0)	Estimands have been clarified for the primary and key secondary endpoints. Details have been added to describe imputation methods for missing Week 52 assessments for standing height, AGV, height Z-Score, sitting height and upper-to-lower body segment ratio.
Final SAP	05-Nov-19	14.2 (12.2)	Terminology for the testing strategy has been changed from “statistically significant “ to “confirmatory”.
Final SAP	05-Nov-19	14.3.3 (12.3.3)	There is now one sensitivity analysis and 2 supplementary analyses: A washout model has been introduced as the sensitivity analysis The completers analysis is now a supplementary analysis (not sensitivity). The analysis excluding data post limb lengthening/growth hormone is now a supplementary analysis (not sensitivity). The random coefficient model sensitivity analysis has been removed.
Final SAP	05-Nov-19	14.7 (12.7)	More detail has been added for subgroup analyses, and subgroups of height Z-score thresholds and AGV thresholds have been added
Final SAP	05-Nov-19	15.1.1 (13.1.1)	A table of the incidence of TEAE’s by SOC, PT and highest CTCAE grade has been added.
Final SAP	05-Nov-19	15.1.1 (13.1.1)	The Achondroplasia-related AE table is now exposure-adjusted
Final SAP	05-Nov-19	15.1.2 (13.1.2)	Events of Special Interest are now Events of Interest.
Final SAP	05-Nov-19	15.1.2 (13.1.2)	Events suggestive of hypotension are removed. Profile of events suggestive of hypotension, and profile of hypersensitivity (SMQ) tables have been removed.
Final SAP	05-Nov-19	15.1.2 (13.1.2)	Incidence and exposure-adjusted ISR tables by duration of ISR have been added.
Final SAP	05-Nov-19	16.1 (14.1)	Bone Age presented by sex and overall. Plots of Z-scores.
Final SAP	05-Nov-19	16.2 (14.2)	Lower limb x-rays: Left and Right leg assessments included. Percent change from baseline removed.

	Study 111-301 Statistical Analysis Plan
---	--

Final SAP	05-Nov-19	16.2 (14.2)	Lumbar spine x-rays: Percent change from baseline removed.
Final SAP	05-Nov-19	16.4 (14.4)	DXA data will be presented separately for each scanner (GE or Hologic). Summaries of fat removed.
Final SAP	05-Nov-19	17.0 (15.0)	Biomarker plots added.
Final SAP	05-Nov-19	18.0 (16.0)	Urine chemistry parameters added.

	Study 111-301 Statistical Analysis Plan
---	--

23 APPENDICES

23.1 Child Behavior Checklist Domains

Domain/Subscale	CBCL 1.5-5	CBCL 6-18
EMOTIONALLY REACTIVE	21. Disturbed by change 46. Twitches 51. Panics 79. Shifts between sad-excite 82. Sudden mood change 83. Sulks a lot 92. Upset by new 97. Whining 99. Worries	
ANXIOUS/DEPRESSED	10. Too dependent 33. Feelings easily hurt 37. Upset when separated 43. Looks unhappy 47. Nervous 68. Self-conscious 87. Fearful 90. Unhappy, sad, depressed	14. Cries a lot 29. Fears 30. Fears school 31. Fears doing bad 32. Must be perfect 33. Feels unloved 35. Feels worthless 45. Nervous, tense 50. Fearful, anxious 52. Feels too guilty 71. Self-conscious 91. Talks or thinks of suicide 112. Worries
WITHDRAWN/DEPRESSED		5. Enjoys a little 42. Rather be alone 65. Won't talk 69. Secretive 75. Shy, timid 102. Lacks energy 103. Sad 111. Withdrawn
WITHDRAWN	2. Acts too young 4. Avoids eye contact 23. Doesn't answer 62. Refuses active games 67. Unresponsive to affection 70. Little affection 71. Little interest 98. Withdrawn	
SOMATIC COMPLAINTS	1. Aches, pains 7. Can't stand things out of place 12. Constipated 19. Diarrhea 24. Doesn't eat well 39. Headaches 45. Nausea 52. Painful bowel movements	47. Nightmares 49. Constipated 51. Feels dizzy 54. Overtired 56a. Aches, pains 56b. Headaches 56c. Nausea 56d. Eye problems

		Study 111-301 Statistical Analysis Plan
	78. Stomachaches 86. Too concerned with neatness 93. Vomits	56e. Skin problems 56f. Stomachaches 56g. Vomiting
SOCIAL PROBLEMS		11. Too dependent 12. Lonely 25. Doesn't get along 27. Jealous 34. Others out to get him/her 36. Accident prone 38. Gets teased 48. not liked 62. Clumsy 64. Prefers younger kids 79. Speech problems
THOUGHT PROBLEMS		9. Can't get mind off thoughts 18. Harms self 40. Hears things 46. Twitching 58. Picks skin 59. Sex parts in public 60. Sex parts too much 66. Repeats acts 70. Sees things 76. Sleeps less 83. Stores things 84. Strange behavior 85. Strange ideas 92. Sleep talks/walks 100. Trouble sleeping
ATTENTION PROBLEMS	5. Can't concentrate 6. Can't sit still 56. Clumsy 59. Quickly shifts 95. Wanders away	1. Acts young 2. Fails to finish 8. Can't concentrate 10. Can't sit still 13. Confused 17. Daydreams 41. Impulsive 61. Poor schoolwork 78. Inattentive 80. Stares blankly
RULE BREAKING BEHAVIOR		2. Drinks alcohol 26. Lacks guilt 28. Breaks rules 39. Bad friends 43. Lies, cheats 63. Prefers older kids 67. Runs away 72. Sets fires 73. Sex problems 81. Steals at home 82. Steals outside home 90. Swearing

	Study 111-301 Statistical Analysis Plan	
		96. Thinks of sex too much 98. Tardy 99. Uses tobacco 101. Truant 105. Uses drugs 106. Vandalism
AGGRESSIVE BEHAVIOR	8. Can't stand waiting 15. Defiant 16. Demands must be met 18. Destroys others things 20. Disobedient 27. Lacks guilt 29. Easily frustrated 35. Gets in fights 40. Hits others 42. Hurts unintentionally 44. Angry moods 53. Attacks people 58. Punishment doesn't change behavior 66. Screams 69. Selfish 81. Stubborn 85. Temper 88. Uncooperative 96. Wants attention	3. Argues a lot 16. Mean to others 19. Demands attention 20. Destroys own things 21. Destroys others' things 22. Disobedient at home 23. Disobedient at school 37. Gets in fights 57. Attacks people 68. Screams a lot 86. Stubborn, sullen 87. Mood changes 88. Sulks 89. Suspicious 94. Teases a lot 95. Temper 97. Threatens others 104. Loud

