9.12.6.7 Child Behavior Checklist

The CBCL 1.5 - 5 and the CBCL 6 - 18 comprise questions addressing symptoms related to mood, behavior issues, and sleep disturbance. It is completed by the parent or primary caregiver. The CBCL 1.5 - 5 years old should be used in children aged 5 to < 6 years old. The CBCL 6 - 18 years old should be used in children aged 6 up to 18 years old. No data will be collected from the language scale, as it is supplemental and not required to calculate any of the behavior measures.

The form requires approximately 15 minutes to complete. The checklist yields scores in the following areas: reactivity, anxiety, depression, somatic complaints, withdrawal, sleep problems, attention problems, and aggressive behavior.

The CBCL assessment will be implemented in those countries where country-specific versions are available.

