15.5 Child Behavior Checklist

The Child Behavior Checklist (CBCL) questionnaire is captured at Screening, Week 26 and Week 52. All summaries will be generated on the Safety Population and include all assessments recorded up to 30 days following treatment discontinuation. Listings will include all reported data.

The CBCL 1.5-5 years old and the CBCL 6-18 years old comprise questions addressing symptoms related to mood, behavior issues, and sleep disturbance. It is completed by the parent or primary caregiver.

The CBCL 1.5-5 years old is used in this study for children aged 5 to < 6 years old. It consists of 100 questions, scored on a three-point Likert scale (0=Not True (as far as you know), 1= Somewhat or Sometimes True, 2=Very True or Often True). The time frame for item responses is the past 2 months.

The CBCL 6-18 years old is used in children aged 6 up to 18 years old. It consists of 113 questions, scored on a three-point Likert scale (0=Not True (as far as you know), 1= Somewhat or Sometimes True, 2=Very True or Often True). The time frame for item responses is the past six months.

	Study 111-301 Statistical Analysis Plan
---	--

Note: No data is collected from the language scale, as it is supplemental and not required to calculate any of the behavior measures.

The checklist yields scores in the following areas:

CBCL 1.5-5	CBCL 6-18

 • Emotionally reactive • Anxious/Depressed • Withdrawn • Somatic Complaints • Attention Problems • Aggressive Behavior 	
 • Anxious/Depressed • Withdrawn/Depressed • Somatic Complaints • Social problems • Thought Problems • Attention Problems • Rule Breaking Behavior

The table in Appendix 23.1 shows how the domains are constructed with regards to the individual questions. The scores for each individual question within a domain are summed to give a domain score.

Each domain score above and total score will be summarized (n, mean, SD, median, 25th and 75th percentile, minimum, maximum) by treatment group at Baseline, Week 26 and Week 52, as will change from baseline at Week 26 and Week 52 (where baseline measures exist).

Where possible, the CBCL 1.5-5 and CBCL 6-18 will be summarized together. If a subject progresses during the course of the study from one version to the next the results will be summarized together and the baseline assessment from the child's first questionnaire (1.5-5) will be referred to when summarizing change from baseline.

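### The CBCL 6-18 key gives item 2 to two different questions, and SAP 15.5 leaves Aggressive Behavior out of the 6-18 domains to be summarised

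*SAP*

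**What the plan says.** SAP 15.5 makes the appendix the scoring rule: "The table in Appendix 23.1 shows how the domains are constructed with regards to the individual questions", and "The scores for each individual question within a domain are summed to give a domain score". Of the 6-18 form it says "It consists of 113 questions, scored on a three-point Likert scale", with answers scored 0, 1 or 2.

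In Appendix 23.1, the 6-18 column has "2. Fails to finish" under Attention Problems and "2. Drinks alcohol" under Rule Breaking Behavior.

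SAP 15.5 then lists the domains for each form in two columns. The 1.5-5 column has six and ends with Aggressive Behavior. The 6-18 column has seven and ends with "Rule Breaking Behavior". The summary instruction follows: "Each domain score above and total score will be summarized", by treatment group at Baseline, Week 26 and Week 52. Appendix 23.1 nevertheless keys an Aggressive Behavior domain in its 6-18 column.

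Protocol 9.12.6.7 gives a single list of CBCL scores for both forms, which includes "somatic complaints, withdrawal, sleep problems, attention problems, and aggressive behavior".

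Protocol 9.12.6 counts the CBCL among the safety variables, and the SAP synopsis says that it is summarised descriptively. Protocol 14.1 and 14.8 and SAP section 4 let the SAP prevail over the protocol. SAP section 4 adds that major differences between the two will be identified in the SAP.

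**The concern.** The appendix is the operative key, so a wrong number in it can pass straight into a program. If items are picked up by number, the answer to item 2 enters both Attention Problems and Rule Breaking Behavior, and the question that really has another number is never scored.

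The second problem lies in the list of outputs. The summary instruction covers the domains listed above it, so a literal reading produces no 6-18 aggression summary. Because the SAP prevails, the protocol's mention of aggressive behavior does not restore it. Nothing in SAP 15.5 marks the omission as intended. A child who moves from the 1.5-5 to the 6-18 form during the study would have a listed baseline aggression score and no listed 6-18 score to compare with it.

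At stake is the accuracy of one behavioural safety score and the presence of another in a placebo-controlled trial in children.

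**Working it through.** The plan states no figure to reproduce on this point. The check is a count of the key and a comparison of lists.

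**Count of the 6-18 key (Appendix 23.1).** Entries per domain:

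- Anxious/Depressed 13
- Withdrawn/Depressed 8
- Somatic Complaints 11
- Social Problems 11
- Thought Problems 15
- Attention Problems 10
- Rule Breaking Behavior 18
- Aggressive Behavior 18

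The total is 13 + 8 + 11 + 11 + 15 + 10 + 18 + 18 = 104 entries with 103 distinct numbers. Number 2 is the only repeat. The same count for the 1.5-5 key gives 60 entries, 60 distinct numbers and no repeat.

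**Which entry is wrong.** The documents do not settle this. Entries ascend within each domain, but order does not help: 4, 6 and 7 are unused in the 6-18 key and would fit in sequence in either list.

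**Size of the scoring error.** If one question is scored in place of another, the error in the domain score is (score of the question used) − (score of the question intended). Each score is 0, 1 or 2, so the error lies between −2 and +2, and it is zero when the two answers agree.

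- If the Attention entry is wrong: 1 of 10 items is affected on a range of 0 to 10 × 2 = 20. The maximum error is 2/20 = 10% of the range.
- If the Rule Breaking entry is wrong: 1 of 18 items is affected on a range of 0 to 18 × 2 = 36. The maximum error is 2/36 = 5.6% of the range.

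**Comparison of the domain lists.**

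- 1.5-5 form: SAP 15.5 has 6 domains and Appendix 23.1 has the same 6.
- 6-18 form: SAP 15.5 has 7 domains and Appendix 23.1 has 8. The missing one is Aggressive Behavior, with 18 of the 104 keyed entries (18/104 = 17%). That is a share of the key, not a measure of error.

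**Sleep problems.** Protocol 9.12.6.7 names this score. Neither SAP 15.5 nor Appendix 23.1 has such a domain for either form. Some sleep questions are scored elsewhere in the 6-18 key: nightmares under Somatic Complaints; sleeping less, sleep talking or walking, and trouble sleeping under Thought Problems.

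**After correction.** The 6-18 key would have 104 distinct items, and the summarised 6-18 domains would go from 7 to 8. No sample size, power or alpha changes.

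**The case against.** The strongest reply is that these are editorial slips which largely correct themselves. Each entry in the key carries its question text, and nobody reading the text would confuse the two questions. On aggression, SAP 15.5 says the two forms will be summarised together where possible, and that listings will contain all reported data. The answers are collected and the 6-18 key exists, so nothing is lost. The analysis is descriptive and touches no confirmatory test. The SAP 15.5 list is also a two-column table, and a last row dropped in conversion to text cannot be excluded.

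Much of this stands, and it limits the size of the point. It does not remove it. The question text helps only a programmer who checks it against the form. The pooling sentence does not say when pooling is possible, and the two aggression scores differ in length: 19 items (0-38) on the 1.5-5 form and 18 items (0-36) on the 6-18 form. Listings are not the by-group summary that the other domains receive. The list shows no visible break, though the source PDF should be checked first.

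A reader might infer more than the documents support:

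- That the main behavioural safety scores are wrong or missing for nearly all children. Most 6-18 domains are untouched, and no age distribution is given. If ages were uniform from 5 up to 11, 15 or 18, the share on the 6-18 form at entry would be 5/6 = 83%, 9/10 = 90% or 12/13 = 92%, but that is an assumption.
- That the Attention score loses sensitivity because alcohol answers are near zero. The documents give no item frequencies and do not show that Attention holds the wrong number.
- That sleep problems belong to the 1.5-5 form. The protocol list is not divided by form.

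**Conclusion.** The point holds in limited form, and the text is wrong as written in two places. The 6-18 key assigns one number to two questions. Followed by number, it misstates a domain score by at most 2 points in a child whose two answers differ. The 6-18 summary list omits one of eight keyed domains, one that the protocol names. Assuming that only one of the two entries numbered 2 is wrong, the other six 6-18 domains are correctly keyed and listed.

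The scoring error arises only if the program uses the printed numbers, and the omission only if the summary list is followed literally. Whether either carries into the total score cannot be said, because SAP 15.5 does not define the total. No efficacy conclusion is affected.

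**What to change.** Before database lock:

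1. Check the Appendix 23.1 key against the printed 6-18 form and correct the duplicated number, so that each item feeds one domain. Confirm that the scoring program uses the corrected key.
2. Add Aggressive Behavior to the 6-18 list in SAP 15.5.
3. Reconcile the sleep-problems score in protocol 9.12.6.7 with SAP 15.5 and Appendix 23.1: either define the domain and its items, or state in the SAP that no such score will be produced.

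The same edit could say which items make up the total score. The cost is a few lines of SAP wording and a check of the scoring program. No new data are needed.
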